5.2.3 Secondary Analyses

All secondary outcomes will be summarized using means and 95% confidence intervals, or percentages and 95% confidence intervals. Longitudinal models will be used to explore the effect of treatment group and time on the HOS and SF-12 patient-reported outcomes. **Table 4** shows the details for the analysis of secondary outcomes.

5.2.4 Planned Exploratory Analyses

Exploratory analyses will be conducted comparing the treatment effects in participants with undisplaced versus displaced femoral neck fractures, and emergent (<8 hours) versus non-emergent (≥ 8 hours) internal fixation. We plan to fit logistic regression models and include treatment by subgroup interactions to assess whether the magnitude of the treatment effect is significantly different between subgroups. **Table 5** shows the details for the exploratory analyses.

5.2.5 Interim Analysis

An interim analysis will not be conducted. The trial will not be stopped early for benefit. The Data Safety and Monitoring Committee (DSMC) will monitor Adverse Events (AEs) and may make recommendations to the Principal Investigators and Steering Committee to stop the study for harm only.

6. DATA MANAGEMENT

6.1 Case Report Forms and Data Entry

The CRFs will be the primary data collection tool for the study. All data requested on the CRF must be recorded. An Electronic Data Capture (EDC) system will be used to submit data to the Methods Centre located at McMaster University. Upon receipt of the data, the personnel at the Methods Centre will make a visual check of the data and they will query all missing data, implausible data, and inconsistencies.

6.2 Data Transmissions

Data will be transmitted from clinical sites to the Methods Centre using an EDC system. The data entry screens in the EDC system will be similar to the paper CRFs. Data integrity will be enhanced by using the EDC system through a variety of mechanisms for checking data at the time of entry including referential data rules, valid values, range checks, and consistency checks against data already stored in the database. Clinical site personnel will be able to view and modify data for participants recruited from their clinical site only. Each time data is submitted or modified, it will be validated by Methods Centre personnel.

6.3 Data Discrepancy Inquiries

Once data are submitted, additional errors will be detected by the program within the EDC system to detect missing data or errors. Clinical site personnel will be notified of these errors through regular quality control reports. Clinical site personnel will be required to respond promptly to each query on the quality control report. To respond to queries study personnel should check the original forms for inconsistency and check other sources of participant records to determine the correction. Clinical site personnel will then modify the data in the EDC system to reflect the correction and resubmit data to the Methods Centre in order to resolve the query.

6.4 Security and Back-Up of Data

All CRFs and specimens must be kept secure in locked cabinets or other enclosures that are accessible only to study personnel. All electronic data must be password-protected and accessible only to study personnel. The Methods Centre will be responsible for backing up all submitted data.

6.5 Quality Control Reports

Each clinical site will regularly receive a quality control report showing the number of each of the following:

1. Participants entered into the trial.
2. Completed follow-ups.
3. Outstanding data queries and clarification requests.
4. Participant's next follow-up visit.
5. Overdue follow-up visits.

Study personnel should review these reports for accuracy and contact the Methods Centre if they identify any discrepancies.

7. ETHICS AND DISSEMINATION

7.1 Research Ethics Approval

This protocol, the consent form template, and the CRFs will be reviewed and approved by McMaster University's Research Ethics Board (REB). The protocol, clinical site-specific informed consent forms, and any participant recruitment material will need to be reviewed and approved by each clinical site's local ethics board. Prior to commencement of the study the clinical site must provide the Methods Centre with a copy of the ethics board approval.

7.2 Consent

Any patients who are deemed to meet all eligibility criteria should be approached to discuss participation in the trial by someone on the study team who is knowledgeable about the trial. In order to obtain informed consent, study personnel should follow the below procedures:

- Present study information in a manner that is understandable to the potential participant/the patient's legal representative.
- Discuss the study with the potential participant/the patient's legal representative and answer any questions he or she asks.
- Allow the potential participant/the patient's legal representative an opportunity to discuss participation with their family, friends, or family physician if desired.
- Confirm that the participant/the patient's legal representative understands the risks and benefits of participating in the study and that their participation is voluntary.
- Complete and obtain signatures for informed consent form and obtain contact information from the participant.

7.3 Confidentiality

Information about study participants will be kept confidential and will be managed in accordance with the below rules:

- All study-related information will be stored securely at the clinical site.
- All study participant information will be stored in locked file cabinets and accessible only to study personnel.
- All CRFs will be identified only by a coded participant number and initials.
- All records that contain participant names, or other identifying information (e.g. consent forms and contact information forms), will be stored separately from the study records that are identified only by the coded participant number and initials.
- All local databases will be password protected.

In the event that a participant revokes authorization to collect or use personal health information (PHI), the clinical site retains the ability to use all information collected prior to the revocation of participant authorization. For participants that have revoked authorization to collect or use PHI, attempts should be made to obtain permission to collect at least vital status (i.e. primary outcome data) at the end of their scheduled study period.

7.4 Access to Data

Only the Methods Centre will have access to the full trial dataset. Data for the primary publication will be analyzed exclusively by the Methods Centre. Requests for access to the full trial dataset for secondary publications are encouraged and can be initiated through a written request to Methods Centre personnel. All requests will be reviewed by the Principal Investigators.

7.5 Protocol Amendments

Any amendments to the study protocol which may affect the conduct of the study, or the potential safety of or benefits to participants (e.g. changes to the study objectives, study design, sample size, or study procedures) will require a formal amendment to the protocol. Any protocol amendments will be approved by the Principal Investigators and will require approval by McMaster University's REB. Clinical sites will also be required to submit amendment requests to their local ethics boards in order to obtain approval for the amendment and to provide the Methods Centre with a copy of this approval. Administrative changes (e.g. minor corrections or clarifications that have no effect on the way the study is conducted) will not need to undergo a formal amendment process and will be communicated to clinical sites when applicable.

7.6 Adverse Event Reporting and Definitions

7.6.1 Adverse Event

An AE is any symptom, sign, illness, or experience that develops or worsens in severity during the course of this study. As FAITH-2 is not assessing patient safety, only AEs that are study outcomes (i.e. fracture-related) will be recorded as per sections 4.8.1 and 4.8.2.

7.6.2 Serious Adverse Event

AEs are classified as serious or non-serious. A SAE is any AE that is any of the following:

- Fatal
- Life threatening
- Requires or prolongs hospital stay
- Results in persistent or significant disability or incapacity
- A congenital anomaly or birth defect
- An important medical event

All SAEs must be recorded and promptly submitted to the Methods Centre.

7.6.3 Unanticipated Problems Resulting in Risk to Participant or Others

Any incident, experience, or outcome that meets all of the following criteria:

- Unexpected in nature, severity, or frequency (e.g. not described in study-related documents such as the ethics-approved protocol or consent form, etc.).
- Related or possibly related to participation in the research (i.e. possibly related means there is reasonable possibility that the incident experience, or outcome may have been caused by the procedures involved in the research).
- Suggests that the research places participants or others at greater risk of harm (including physical, psychological, economic, or social harm).

All unanticipated problems resulting in risk to participants or others must be recorded and promptly submitted to the Methods Centre.

7.7 Reporting of Serious Adverse Events and Unanticipated Problems Resulting in Risk to Participants or Others

All fracture-related AEs, SAEs, and unanticipated problems resulting in risk to participants or others are to be reported to the Methods Centre immediately.

7.7.1 Clinical Site Reporting: Notifying the Methods Centre

All fracture-related AEs and SAEs must be reported to the Methods Centre by completing the AE form and submitting it to the Methods Centre. The clinical site will keep a copy of this form on file at the clinical site. Significant new information on ongoing SAEs should be provided promptly to the Methods Centre by updating the form. Unanticipated problems resulting in risk to participants or others are to be reported to the Methods Centre.

7.7.2 Clinical Site – Institutional Review Board and Research Ethics Board Reporting

Clinical sites are responsible for reporting fracture-related AEs, SAEs and unanticipated problems resulting in risk to participants or others to their local ethic boards. Clinical sites are responsible for complying with their local ethic boards reporting requirements. Copies of each report and documentation of ethic board notification and receipt will be kept in the clinical site's study file.

7.8 Potential Risks to Participants

Surgeons worldwide are currently using both surgical techniques (cancellous screws and SHS). Both implants have been used for over five decades in the management of hip fractures. As with any surgical procedure of the lower extremity, potential risks include wound infection, deep vein thrombosis, neurovascular injury, and death. Given that all eligible patients require surgery for their acute fracture, there is no anticipated increased surgical risk for study participants. Similarly, the safety of vitamin D₃ supplementation is well established, and 4,000 IU per day is within the tolerable daily dose according to Health Canada.³⁶ Participants will be monitored for all SAEs and fracture-related AEs following treatment across the surgical and nutritional arms. The DSMC will review SAEs and fracture-related AEs at regular intervals.

7.9 Dissemination Policy

Results from the primary manuscript will be submitted for publication regardless of whether or not there are significant findings. Every attempt will be made to ensure that the amount of time between completion of data collection and release of study findings are minimized.

7.10 Ethical Considerations

This study is to be conducted according to US and international standards of Good Clinical Practice and International Conference on Harmonization guidelines, applicable government regulations, and institutional research policies and procedures.

8. STUDY COMMITTEES

8.1 Steering Committee

The Steering Committee is comprised of orthopaedic surgeons, vitamin D experts, a statistician, and research methodologists. The Steering Committee will provide guidance and direction to the overall trial.

8.2 Data Safety and Monitoring Committee

The DSMC is comprised of 3 members who remain completely independent of the study investigators. The DSMC members include a biostatistician (Chair) and two orthopaedic surgeons with prior trial experience. The DSMC will review accumulated safety data (i.e. SAEs and fracture-related AEs) from the trial and advise the Principal Investigators and the Steering Committee on items related to participant safety.

8.3 Central Adjudication Committee

The CAC will be comprised of four orthopaedic surgeons with prior adjudication experience and they will independently adjudicate the following:

- Situations where eligibility is in doubt
- Radiographic characteristics and quality of the surgery
- Patient important outcomes that define the primary outcome (re-operation, femoral head osteonecrosis, severe femoral neck malunion, or nonunion)
- Fracture healing complications
- Radiographic fracture healing

All clinical sites will submit X-Rays and any additional imaging studies (such as a hip MRI or other advanced imaging studies) to be included in the adjudication process (**Figure 7**). Clinical notes may also be requested. Any disagreements between the CAC members will be resolved during regular conference calls. If consensus cannot initially be reached, additional information will be requested from the clinical site to clarify areas of uncertainty.

Table 1: Schedule of Events

Assessment	Screening	Enrollment (Baseline)	Surgery	Post-operative	Week 6	Month 3	Month 6	Month 9	Month 12
Informed Consent	X								
Medical History	X								
AP & Lateral X-Rays of Proximal Femur	X			X	X	X	X	X	X
Physical Exam/Injury Assessment	X								
Screening Form	X								
Randomization Form		X							
Pre-Operative Form		X							
Surgery (SHS or Cancellous Screws)			X						
Surgical Forms			X						
Hospital Discharge Form				X					
Vitamin D or Placebo Supplementation**				X	X	X	X		
Follow-up Visit Forms				X	X	X	X	X	X
Assessment for Re-Operations				X	X	X	X	X	X
Assessment of Fracture Healing Complications					X	X	X	X	X
Assessment of Fracture Healing					X	X	X	X	X
Hip Outcome Score (HOS)				X*	X	X	X	X	X
Short Form-12 (SF-12)				X*	X	X	X	X	X
Assessment of Fracture Healing of the Ipsilateral Femoral Shaft Fracture***					X	X	X	X	X
Assessment for Fracture-Related Adverse Events			X	X	X	X	X	X	X
Assessment for Serious Adverse Events			X	X	X	X	X	X	X
Assessment for Planned Re-operations									X

*Asks about participant’s function prior to their hip fracture.

** Nutritional supplementation will be administered upon hospital discharge or within two weeks of the participant’s surgery, whichever comes first. Ideally, participants should be administered the nutritional supplementation as soon as possible following their surgery to repair their femoral neck fracture.

***For participant’s with an ipsilateral femoral shaft fracture.

Table 2: Sample Size Estimates

		Relative Risk Reduction from the SHS and vitamin D supplementation					
		20%	25%	30%	33%	35%	40%
Incidence of Patient Important Outcomes in the control groups	20%	2994	1890	1294	1060	936	706
	25%	2266	1434	984	808	714	540
	30%	1782	1130	778	638	566	428
	35%	1436	914	630	518	460	348
	40%	1178	752	520	428	380	288

- Total sample size required to achieve 80% power for the independent comparisons of the SHS versus cancellous screws AND vitamin D supplementation versus placebo.
- Grey highlighted boxes denote scenarios where we have more than 80% power (alpha=0.05, 2-sided) to detect the hypothesized difference, given our proposed sample size of 808.
- Control groups: cancellous screws and placebo supplementation

Table 3: Summary of Primary Outcome Analyses

Variable/Outcome	Hypothesis for Surgical Treatments	Hypothesis for Nutritional Supplementation	Outcome Measures	Method of Analysis
Re-operation	The incidence of re-operation, femoral head osteonecrosis, severe femoral neck malunion, or nonunion will be lower in patients receiving a SHS compared to cancellous screws.	The incidence of re-operation, femoral head osteonecrosis, severe femoral neck malunion, or nonunion will be lower in patients receiving vitamin D versus placebo.	Re-operation anytime within 12 months	Chi-square statistic with independent comparison for the surgical treatments and nutritional treatments (alpha=0.05)
Femoral head osteonecrosis			Evidence of femoral head osteonecrosis on X-Rays or MRI	
Severe malunion			Evidence of severe femoral neck malunion on X-Rays	
Nonunion			Failure of the fracture to progress towards healing defined as a Radiographic Union Score for Hip (RUSH) ^{41,42} score below a pre-determined threshold specific for nonunion at 6 months or greater post-injury	

[figure not shown]
*The primary outcome is a composite of re-operation, femoral head osteonecrosis, severe femoral neck malunion, or nonunion.

Table 4: Summary of Secondary Analyses

Variable/Outcome	Hypothesis for Surgical Treatments	Hypothesis for Nutritional Supplementation	Outcome Measures	Method of Analysis
HRQL and function	HRQL and function will be better in patients receiving SHS versus cancellous screws.	HRQL and function will be better in patients receiving vitamin D versus placebo.	HOS and SF-12	Summary statistics of means and confidence interval Longitudinal modeling to include treatment and time
Fracture healing complications	Rates of fracture healing complications will be lower in patients receiving SHS versus cancellous screws.	Rates of fracture healing complications will be lower in patients receiving vitamin D versus placebo.	Evidence of complications reported by patients or evident on X-Rays	Summary statistics of proportions Chi-square statistic with independent comparison for the surgical treatments and nutritional treatments
Fracture healing	Fractures will heal faster in patients receiving SHS versus cancellous screws.	Fractures will heal faster in patients receiving vitamin D supplementation.	A fracture will be considered as healed when there is obliteration of the fracture line by newly formed bone along the cortices and within the trabecular bone on anterior-posterior and lateral X-rays	Time to event analysis with treatment group as an independent variable

[figure not shown]
Table 5: Summary of Exploratory Analyses

Fracture/Surgical Characteristics	Hypothesis for Surgical Treatments	Hypothesis for Nutritional Supplementation	Outcome Measures	Method of Analysis
Undisplaced versus displaced femoral neck fractures	The magnitude of treatment effect favouring SHS will be higher in displaced fractures vs. undisplaced fractures	The magnitude of treatment effect favouring vitamin D will be higher in displaced fractures vs. undisplaced fractures	Composite primary outcome as above (reoperation, femoral head osteonecrosis, severe femoral neck malunion, and nonunion)	Logistic regression models with an interaction term between treatment and femoral neck displacement
Emergent (<8 hours) versus non-emergent (≥8 hours) internal fixation	The magnitude of treatment effect favouring SHS will be higher in fractures treated emergently vs. non-emergently.	Not Applicable	Composite primary outcome as above (reoperation, femoral head osteonecrosis, severe femoral neck malunion, and nonunion)	Logistic regression models with an interaction term between treatment and internal fixation type

Figure 1: Blood Supply to the Femoral Head

[figure not shown]
The femoral head and neck are perfused by a ring of small blood vessels. These fragile capsular vessels are most vulnerable to injury at the femoral neck and are frequently torn during the fracture. Disrupting the local blood supply leads to femoral head osteonecrosis (bone death) and femoral neck nonunion (the fracture does not heal)

Figure 2: Multiple Cancellous Screws

2a Diagram of screw fixation
2b X-ray depiction of screw fixation

Figure 3: Sliding Hip Screw

- 3a Diagram of sliding hip screw
- 3b X-ray depiction of sliding hip screw

[figure not shown]
Figure 4: Recruitment and Follow-Up Schedule

Figure 4: Recruitment and Visit Schedule (continued)

[figure not shown]

Figure 5: Retention Strategies

1) We will exclude individuals who are likely to present problems with follow-up (see exclusion criteria).

2) At the time of randomization, as well as their own address and phone number, each participant will provide the name and address of their primary care physician, and the name, address and phone number of three people at different addresses with whom the participants does not live who are likely to be aware of the participant's whereabouts. The research coordinator will confirm that these numbers are accurate prior to the participant's discharge from hospital.

3) Participants will receive reminders for upcoming clinic visits from local study personnel.

4) Follow-up schedules will coincide with normal surgical fracture clinic visits.

[figure not shown]
5) Study personnel will contact participants no less frequently than once every three months to maintain contact and obtain information about any planned change in residence.

6) If a participant refuses to return for a follow-up assessment, study personnel will reduce the burden of the study assessments and aim to have the participant complete the primary outcome only.

Sprague et al⁴⁶

Figure 6: Unblinding of Clinical Site Personnel for Emergency Medical Management

1. In the event of a medical emergency that directly affects the health status of the participant, it may become necessary to unblind allocation status to determine the specific treatment the participant has received while enrolled in the study. A medical emergency is defined as an event which necessitates immediate attention regarding the treatment of a participant.
2. Clinical sites are instructed to contact the Methods Centre and provide details of the medical emergency as soon as possible after the event. At no time will the participant's health be compromised or medical treatment delayed.
3. When a request for unblinding is received by the Methods Centre, the Research Coordinator (or designee) is responsible for contacting the Principal Investigator (or designee).

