4.8.2 Secondary Outcome

The secondary outcomes will include:

1. HRQL and patient-reported function as measured by the:
 - Short Form-12 (SF-12)⁴³ which measures self-reported quality of life through an 8-domain profile of functional health and well-being, physical and mental health summary measures and a preference-based health utility index.
 - Hip Outcome Score (HOS)⁴⁴ which measures self-reported functional status through 28 items and two sub-scales that pertain to activities of daily living (ADLs) or higher level activities such as those necessary to participate in sports.
2. Fracture healing complications: These will include wound healing problems, infection (superficial and deep), hardware failure, hardware breakage, painful hardware, and peri-prosthetic fracture.
3. Radiographic fracture healing: The date of healing will be determined by the Central Adjudication Committee (CAC). They will consider a fracture as healed when there is obliteration of the fracture line by newly formed bone along the cortices and within the trabecular bone on anterior-posterior and lateral radiographs.

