4.9 Frequency and Duration of Follow-Up

Participants will be followed for a period of 12 months post-surgery (**Figure 4**). Participant follow-up visits will occur at enrollment (baseline), post-operative (24 hours to 14 days window), 6 weeks (2 week to 8 week window), 3 months (2 to 4 month window), 6 months (5 to 7 month window), 9 months (7 to 11 month window), and 12 months (11 months or greater window) post-surgery.

The **Schedule of Assessments (Table 1)** details the requirements and procedures for each visit. All study outcomes (as defined in sections 4.8.1 and 4.8.2) will be documented on the case report forms (CRFs) at each follow-up visit.

Additionally at all follow-up visits the participant will complete the SF-12 and HOS questionnaires. At the post-surgery follow-up visit participants will answer all questionnaires based on their pre-injury status. Questionnaires for subsequent follow-up visits will be answered based on the participant's current status at the time of follow-up.

For participants who have an ipsilateral femoral shaft fracture at each follow-up visit we will document: 1) the time to radiographic fracture healing of the ipsilateral femoral shaft; 2) re-operation; and 3) fracture-related complications including compartment syndrome, wound healing problems, infection (superficial or deep), hardware failure, hardware breakage, malunion, nonunion, and prolonged pain at the fracture site.

Serious adverse events (SAEs) will also be documented at each visit. X-rays of the participant's fractured hip are required at enrollment (baseline), post-surgery, and at, 6

weeks, 3 months, 6 months, 9 months, and 12 months post-surgery. As the primary outcome includes radiographic outcomes, it is important that X-rays be obtained at all follow-up visits. MRI or other advanced imaging studies are not required and may be ordered at the discretion of the attending surgeon. Clinical notes may also be requested. If additional imaging studies are obtained, they will be sent to the Methods Centre for outcome adjudication. In addition, at the 12-month follow-up visit, any re-operations that may be planned for the participant will be documented.

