9.4 Radiographic Fracture Healing

Table 20: Radiographic Fracture Healing

Variable	Variable	Surgical Treatment X N=	Surgical Treatment Y N=	Nutritional Supplementation X N=	Nutritional Supplementation Y N=	Total N=
Time of Radiographic Fracture Healing, mean (SD) (months)	Adjudicated Data					
Time of Radiographic Healing of Ipsilateral Femoral Shaft Fracture, mean (SD) (months)	Adjudicated Data					

Figure 13: Kaplan-Meier Curves for Radiographic Fracture Healing (Significant Interaction Between Implant Type and Supplementation Present)

[figure not shown]

Figure 14: Kaplan-Meier Curves for Radiographic Fracture Healing by Surgical Treatment Group (No Significant Interaction Between Implant Type and Supplementation Present)

[figure not shown]

Figure 15: Kaplan-Meier Curves for Radiographic Fracture Healing by Nutritional Supplementation Group (No Significant Interaction Between Implant Type and Supplementation Present)

[figure not shown]

Figure 16: Kaplan-Meier Curves for Radiographic Healing of Ipsilateral Femoral Shaft Fracture (Significant Interaction Between Implant Type and Supplementation Present)

[figure not shown]

Figure 17: Kaplan-Meier Curves for Radiographic Healing of Ipsilateral Femoral Shaft Fracture by Surgical Treatment Group (No Significant Interaction Between Implant Type and Supplementation Present)

[figure not shown]
[figure not shown]

Figure 18: Kaplan-Meier Curves for Radiographic Healing of Ipsilateral Femoral Shaft Fracture by Nutritional Supplementation Group (No Significant Interaction Between Implant Type and Supplementation Present)

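### SAP 9.4 plans Kaplan-Meier curves and a mean (SD) for radiographic healing, which is known only to lie between two films; the plan gives no dating rule and makes no allowance for interval censoring

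*Combined protocol and SAP*

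**What the plan says.** Radiographic healing is a secondary outcome. Protocol 4.8.2 has the Central Adjudication Committee (CAC) determine the date of healing from two radiographic views. It does not say whether that date is the first film showing healing, a midpoint or something else.

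Protocol 4.9 schedules films after surgery at 6 weeks and 3, 6, 9 and 12 months. The windows are 2 to 8 weeks, 2 to 4 months and 5 to 7 months for the first three, then "9 months (7 to 11 month window), and 12 months (11 months or greater window) post-surgery". Additional imaging is at the surgeon's discretion and is sent for adjudication.

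Protocol Table 4 states a timing hypothesis for each factor: "Fractures will heal faster in patients receiving SHS versus cancellous screws" and "Fractures will heal faster in patients receiving vitamin D supplementation". The method is "Time to event analysis with treatment group as an independent variable". No model, tie rule or type of censoring is named.

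SAP 9.4 consists of a table and figure titles. Table 20 gives a mean (SD) healing time in months. Figures 13 to 15 are Kaplan-Meier displays, for example "Kaplan-Meier Curves for Radiographic Fracture Healing by Surgical Treatment Group". The only SAP sentence describing a time-to-event analysis of healing is in SAP 9.5 and concerns the ipsilateral shaft fracture. SAP 10.0 assigns missing data to multiple imputation and does not mention interval censoring.

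**The concern.** A hip that is unhealed on one film and healed on the next healed at some point in between. Kaplan-Meier curves and a mean (SD) need a single exact time for each patient. If that time is the first healed film, every healing time is placed too late, by an amount that depends on the visit schedule. For an endpoint whose hypotheses are about speed of healing, the estimated curves and medians then partly reflect when patients were X-rayed. The hazard ratio can also be distorted, in a way that depends on dating and tie rules the plan leaves open. The mean (SD) has a further problem: a hip not healed by the last film has no healing time, so it cannot enter the mean.

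**Working it through.** **The plan's own figure.** No sample size, power, healing rate or effect size is given for healing. The only sample-size figure, 808, belongs to the primary composite: 25% versus 25% × 0.67 = 16.75%, 80% power, two-sided 0.05. The continuity-corrected two-proportion formula gives 404 per group, so 808 in total, and 808 / 0.90 = 897.8, rounded up to 898. Nothing below changes these numbers.

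**Width of the intervals (protocol 4.9).**
- Nominal gaps: 3 − 1.5 = 1.5 months, then 6 − 3 = 9 − 6 = 12 − 9 = 3 months.
- Largest gap within windows, 3-month to 6-month film: 7 − 2 = 5 months.
- Largest gap within windows, 6-month to 9-month film: 11 − 5 = 6 months.
- The 12-month window has no upper limit. A missed visit widens any gap, and discretionary imaging may narrow some.

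**Effect on the estimates.** The documents give no healing distribution, so one was assumed:
- 808 patients, 404 per group; 5% missed visits; 10% loss to follow-up.
- Weibull healing times with control median 3, 4 or 6 months and shape 1, 1.5 or 2.5; true HR 1.0, 1.25, 1.5 or 2.0.
- Films at nominal times, or triangular or uniform within the windows.
- Healing dated to the first film showing it.
- 200 simulated trials per scenario (60 for the interval-censored Weibull fit).

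Selected results, control median 4 months:

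| Visits, shape | Cox, true times | Cox, film date (Efron) | Interval-censored | Control median, true → Kaplan-Meier |
|---|---|---|---|---|
| Triangular, 1.5 | 1.006 | 1.005 | 0.998 | 4.00 → 5.95 |
| Triangular, 1.5 | 1.248 | 1.223 | 1.240 | 3.98 → 5.95 |
| Uniform, 1.5 | 1.234 | 1.203 | 1.241 | 3.97 → 5.93 |
| Triangular, 1.0 | 1.504 | 1.476 | 1.516 | 4.00 → 5.96 |
| Triangular, 1.5 | 1.502 | 1.443 | 1.498 | 4.02 → 5.96 |
| Nominal, 2.5 | 1.501 | 1.341 | 1.522 | 4.00 → 6.00 |
| Triangular, 1.5 | 2.008 | 1.856 | 2.018 | 3.99 → 5.94 |

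*Curves.* Medians were late in every scenario. At true HR 1.0 to 1.5 the delay ran from 3.36 − 2.67 = 0.69 to 6.00 − 3.39 = 2.61 months. The one smaller value was at HR 2.0 with nominal visits (treated arm, 3.00 − 2.52 = 0.48).

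*Hazard ratio.* A true 1.5 read 1.34 to 1.49 with Efron ties under any visit pattern, and 1.35 to 1.48 with either tie rule when film dates vary within the windows. A true 1.25 read 1.20 to 1.23. The relative shrinkage runs from 1 − 1.486/1.504 = 1.2% to 1 − 1.341/1.501 = 10.7%. In a single large-sample check, midpoint dating moved the estimates little (for example 1.452 to 1.477 for a true 1.5).

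*Other effect measures.* These moved either way. The difference in restricted mean healing time to 11 months went from 0.82 to 0.88 in one scenario and from 1.14 to 0.96 in another. With a 3-month control median and triangular visits, the median difference grew from 3.01 − 2.30 = 0.71 to 4.93 − 3.28 = 1.65 months. With nominal visits at HR 1.25 it vanished, from 3.98 − 3.44 = 0.54 to 6.00 − 6.00 = 0.

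*Power at HR 1.25, N=808.* With dates known exactly, power was 0.84 to 0.91; with film dates and Efron ties it was 0.70 to 0.83. Part of that gap is information the schedule does not collect, so the fairer comparator is a model that uses the intervals. In a separate run of 1,000 trials (shape 1.8, control median 4.5 months), power was 80% for the film-date Cox model, 85% interval-censored and 88% with exact dates. The 5-point gap became about 3 points at shape 1.2 and about 7 at a 7-month median. Against a grouped-time complementary log-log model the loss was about 1 to 6 points.

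*Null.* At true HR 1.0 the estimate was 1.00 to 1.01 and the rejection rate did not exceed 0.05.

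*Better models.* The interval-censored Weibull model gave 1.24 to 1.26 for a true 1.25 and 1.48 to 1.54 for 1.5. The complementary log-log model gave 1.24 to 1.26 and 1.49 to 1.50.

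**The case against.** The strongest reply is that much of the fault is inferred from silence. An interval-censored model would satisfy the wording of protocol Table 4, and nothing says the film date is the event date. A reader might infer that the plan commits to an ordinary right-censored Cox model; the documents do not support that. What stands is SAP 9.4: Kaplan-Meier figures and a mean (SD), with no dating rule and no provision for intervals.

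A reader might also infer that the treatment effect is always understated. That holds for a Cox hazard ratio with Efron or Breslow ties, not for mean or median differences. With nominal dates and discrete-logistic ties the estimate is inflated instead (a true 1.5 read 1.71 to 1.76). The largest shrinkage (a true 1.5 reading 1.22 to 1.38) requires both coding to nominal visits and Breslow ties, and no passage plans that combination.

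The size is modest. At HR 1.25 the bias is ln(1.25/1.22) = 0.024, about one third of the standard error of 0.074 at N=808. The shell of SAP Table 2 prints 43, 43 and 86. If 86 is the number analysed, which is an inference, the standard error is about 0.074 × √(808/86) = 0.23, and power at HR 1.25 is about 15% versus 17%, so the choice of model would hardly affect power. The delay in the curves would remain.

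Finally, the interval-censored Weibull model was fitted to Weibull data, which favours it. The complementary log-log model does not assume a Weibull shape and also recovered the true values.

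**Conclusion.** The point holds in a limited form. SAP 9.4 displays and summarises as an exact time something observed only to an interval of 1.5 to 3 months nominally, and up to 5 or 6 months within the windows. If healing is dated to the first healed film, medians and curves run late by about 0.7 to 2.6 months at true HR 1.0 to 1.5. A film-date Cox hazard ratio shrinks by about 1 to 11%, and about 1 to 7 points of power are lost at HR 1.25 with N=808, compared with a model that uses the intervals. These sizes rest on the assumed Weibull distributions, the assumed dating rule and the assumed spread of visits. The mean (SD) cannot include unhealed hips under any of these assumptions.

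This does not threaten the trial's main conclusion. It is a secondary endpoint, both arms share the schedule, there is no bias under the null, and the primary analysis and the 808/898 do not depend on it. The change is worth making because it is cheap and closes choices best fixed before unblinding.

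**What to change.** In SAP 9.4, with a matching line in protocol Table 4:

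1. State how the CAC dates healing, and record for each hip the last film not healed and the first film healed.
2. Estimate each treatment effect with an interval-censored proportional hazards model, or a grouped-time complementary log-log model by visit.
3. Plot non-parametric interval-censored (Turnbull-type) curves in Figures 13 to 15, keeping Kaplan-Meier by film date as a descriptive display only.
4. Replace the mean (SD) in Table 20 with a summary that includes unhealed hips, such as the proportion healed by each visit or the median from the interval-censored curve.

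The cost is SAP wording, somewhat more programming and a curve less familiar to readers. No new imaging is needed, because sites already submit the films. The last-not-healed date may still have to be extracted from the adjudication records, since the only adjudication output the protocol names for healing is a healing date.
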